### **7.11.2 Time to event Analysis**

Time to treatment failure and time to first flare as assessed by new BILAG 2004 index flare definition will be summarized. For those time to event endpoints, if necessary, the point estimate and its 90% confidence interval for the hazard ratio of each active treatment arm versus placebo will be calculated based on the Cox proportional hazards models. In addition, the distribution of time to the occurrence of event will be estimated using Kaplan-Meier method. The analysis will be based on the Efficacy Analysis Population.

Treatment failure is defined as non-protocol treatment i.e., new or increased immunosuppressive treatment or antimalarials; or parenteral corticosteroids; or protocol prohibited dose of oral corticosteroid; or premature discontinuation from study treatment.

#### **7.11.4 Immunogenicity and PK/Efficacy/Safety**

A listing of drug concentration with immunogenicity assessment at each pre-specified time point will be provided for each individual subject who has positive immunogenicity response (laboratory reported ADA positive).

Efficacy listings for all anti-drug antibody positive subjects (laboratory reported ADA positive) may be provided.

Listings of AEs, SAEs, and local injection site events for all anti-drug antibody positive (laboratory reported ADA positive) subjects will be provided.

A list of neutralizing positive subjects (subjects with at least one ADA positive sample relative to baseline with neutralizing antibodies detected) will be provided also.

Depending on the incidence of ADA positive relative to baseline observed in SLE patients within this trial, individual plots of Ctrough with ADA status may be generated for all subjects with ADA positive relative to baseline.

#### **7.11.5 Exposure-Response Analysis**

The PK data obtained from this study may be pooled with data from other studies to perform an integrated population PK (PPK) analysis (including assessment of covariate effects on PK), as well as exposure-response analysis for selected safety and efficacy endpoints. These analyses will be described in a separate report(s).

#### **7.11.6 Analysis for the PK Sub-Study**

As specified in the amendment 9 of the protocol, participation for PK sub-study is voluntary. While there is no minimum required number of subjects, every effort will be made to enroll approximately 4 subjects/arm in the ST study (ie approximately 20 subjects total) and approximately 6 subjects/arm in the LTE (ie approximately 30 subjects total). This sample size is expected to provide sufficient data to adequately estimate PK parameters for lulizumab in this patient population. Subjects will be asked to read, understand, and sign an informed consent form designed for the purpose of collecting the additional PK/RO samples.

#### **Pharmacokinetics Analysis**

All PK summaries and analysis will be done separately for first dose exposure and steady state exposure:

Summary statistics will be provided for all PK parameters by treatment groups for first dose exposure and steady state exposure. Geometric means and coefficients of variation (CV) will be

provided for Cmax, AUC(TAU), and C(Day15). Medians and ranges will be provided for Tmax. Mean and standard deviation may be provided for T-HALF and CLT/F. Additionally, scatter plots of AUC(TAU), Cmax and C(Day 15) versus dose for the three every 2 weeks treatment groups (1.25 mg, 5 mg and 12.5 mg every 2 weeks) to assess the dose-dependency. All plots will be provided separately for first dose exposure and steady state exposure.

A statistical analysis using a power model will be performed to assess dose proportionality in AUC(TAU), Cmax and C(Day 15) for only the three every 2 weeks treatment groups (1.25 mg, 5 mg and 12.5 mg every 2 weeks). The analyses will be carried out separately for first dose exposure and steady state exposure.

In addition, a listing will be provided for all PK parameters and lulizumab concentration.

#### **Receptor Occupancy Analysis:**

Medians and ranges will be presented for RO by Day for all treatment groups in each subgroup. Box plots of RO by Day will be provided for all treatment groups in ST and LTE.

#### **Immunogenicity Analysis:**

The number and percentage of subjects will be summarized for each treatment, and the corresponding antibody titer values will be listed. Exploratory plots or analysis might be conducted to evaluate the impact of immunogenicity on PK of lulizumab.

All other safety, efficacy and biomarker observations that are being planned in the main study protocol will be reported in the clinical study report of the main study.

## **8 CONVENTIONS**

### **8.1 Calculations of Key Measures**

#### **8.1.1 Evaluation of BICLA response**

BICLA response is defined based on the following components:

- British Isle Lupus Assessment Group improvement, defined as BILAG ‘A’s at Baseline improved to ‘B’/‘C’/‘D’, and BILAG ‘B’s at baseline improved to ‘C’/‘D’, and no BILAG worsening in other BILAG organ systems such that there are no new BILAG ‘A’s or greater than 1 new BILAG ‘B’; and,
- No worsening in the SLEDAI-2K total score compared to Baseline (defined as no increase in SLEDAI total score); and,
- No worsening in the physician’s global assessment (MDGA) of disease activity (“no worsening” is defined as less than 10% worsening, equivalent to a 10mm increase on a 100mm visual analog scale [VAS]) compared to Baseline; and,
- No changes in concomitant medications according to the following criteria:
  - No increase of or addition of a new immunosuppressant agent (azathioprine, methotrexate, anti-malarial) over baseline levels

- No increase in corticosteroid dose above baseline level outside of those allowed per protocol.

If a subject failed any of the above criteria above, the BICLA response status of the subjects will be set to non-responder.

For the determination of missing BICLA response status, all subjects who prematurely discontinue from the study medication will be imputed as non-responder at all scheduled efficacy visits subsequent to the point of discontinuation.

If any subject has at most one missing component (e.g. MDGA for BICLA) at a given efficacy visit not due to premature discontinuation, the component-wise response status will be imputed based on the following rules.

- If the given visit is not the last scheduled efficacy visit (Day 169), imputation will depend on the observed responses from the immediate previous efficacy visit and the immediate next efficacy visit within 28 days of the current visit date.
- If the given visit is the last scheduled efficacy visit (Day 169), the imputation will depend on the observed responses at the previous 2 consecutive efficacy visits (within 56 days).
- If a subject has response (at component level) at both efficacy visits, the missing response status at current visit will be imputed as responder. Otherwise, response status will be set to non-responder.

The BICLA response status (composite) for a subject who has more than one component (e.g. MDGA and SLEDAI-2K are missing for BICLA) missing at a given efficacy visit not due to premature discontinuation will be imputed as non-responder.

After any imputation above or none, if for some reason the BICLA response status still cannot be determined, including the case where baseline data is missing, then its value will be set to non-responder.

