1.3.2 Secondary Objectives

Short-term period Part 1 only:

- To evaluate the safety and RO when 6 to 10 subjects per arm reach 29 days (4 weeks).

Short-term period Part 1 and Part 2:

To assess:

- The safety and tolerability of treatment with BMS-931699 in patients with active SLE
- The proportion of patients who meet response criteria for the SLE Responder Index(4) [SRI(4)], SRI(5) and SRI(6) at Day 169.

Note: An SRI(X) Response is defined as:

- a reduction in Day 1 SLEDAI-2K disease activity score of $\geq X$ points;
- no worsening of disease (defined as an increase of ≥ 30 mm on a 100mm VAS from Day 1 as measured by the MDGA; and
- no new BILAG-2004 Index A organ system score and no more than one new or worsening BILAG-2004 Index B organ system scores

- The proportion of patients with SLE Responder Index [SRI(4), SRI(5) and SRI(6)] at Day 85.
- The proportion of patients with a BICLA response at Day 85.
- The improvement in the extent of cutaneous and mucous membrane activity, as measured by the Cutaneous Lupus Erythematosus Disease Area and Severity Index (CLASI) at Day 85 and Day 169

- Joint tenderness and swellings as measured by the by American College of Rheumatology (ACR)28 at Day 85 and Day 169
- The other indices of SLE activity measured at Days 29, 57, 85, 113, 141 and 169 including:
 - The change from baseline in overall BILAG-2004 score. A major response is defined as described in Yee et al 2010 (A=12, B=8, C=1, D/E=0).¹¹
 - The change in overall Systemic Lupus Erythematosus Disease Activity Index 2K score (SLEDAI 2K)
 - The change from baseline in Physician's Global Assessment of disease activity (MDGA) score
- The systemic exposure of BMS-931699 in patients with SLE
- The cumulative corticosteroids use and immunosuppressants use over time
- The immunogenicity of BMS-931699
- Serum biomarkers C3, C4, anti-double-stranded deoxyribonucleic acid (anti-dsDNA), anti-nuclear antibody (ANA) and other autoantibodies at Day 85 and Day 169
- The pharmacodynamics (PD) of BMS-931699, including assessments potentially associated with target engagement [including receptor occupancy (RO)].

Note: Although all efforts must be made to collect all RO samples required per protocol, it may not be possible for a site to obtain samples from subjects located in certain participating regions due to stability and processing issues. Site **MUST** consult with the Medical Monitor prior to deciding not to collect RO samples.

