Adverse Event Reporting	X	
Monitor for Serious Adverse Events	X	All SAEs must be collected from the date of subject's written consent until 42 days post discontinuation of dosing or completion of subject's participation in the study if the last scheduled visit occurs at a later time.

Table 5.1-2: Short-Term Procedural Outline (IM128027)

Procedure / Visit Day (± 2 days is allowed for all visits, including Day 1)	D 1	D 15	D 29	D 57	D 85	D 113	D 141	EOT / D 169	FU D 42* (FUP no.1 visit)	Dosing Every Week (in addition to Visits assessing disease activity)	Notes
Confirm inclusion and exclusion criteria are met prior to dosing	X										
Efficacy Assessments											
BILAG-2004 Index	X		X	X	X	X	X	X	X		See Appendix 4
SLEDAI 2K	X		X	X	X	X	X	X	X		See Appendix 5
Physician's Global Assessment of Disease Activity (MDGA)	X		X	X	X	X	X	X	X		
Subject's Global Assessment of Disease Activity (PGA)	X		X	X	X	X	X	X	X		
ACR28 - joint count	X		X	X	X	X	X	X	X		
FACIT - F	X	X	X	X	X	X	X	X	X		See Appendix 9
CLASI	X		X	X	X	X	X	X	X		See Appendix 6
SLICC/ACR Damage Index	X							X			See Appendix 7
SF-36	X		X	X	X	X	X	X	X		See Appendix 8
Coomb's test-direct	X		X	X	X	X	X	X	X		
Safety Assessments											
Targeted PE	X	X	X	X	X	X	X	X	X		See Section 5.3.4 of the protocol for more details

Table 5.1-2: Short-Term Procedural Outline (IM128027)

Table 5.1-2: Short-Term Procedural Outline (IM128027)

Procedure / Visit Day (± 2 days is allowed for all visits, including Day 1)	D 1	D 15	D 29	D 57	D 85	D 113	D 141	EOT / D 169	FU D 42* (FUP no.1 visit)	Dosing Every Week (in addition to Visits assessing disease activity)	Notes
Laboratory safety tests	X	X	X	X	X	X	X	X	X		Include blood and urine samples. Subjects are required to fast for at least 10 hours prior to the collection of specimens for clinical laboratory tests.
CMV and EBV					X			X			
Adverse Event Reporting											
Monitor for Non-Serious Adverse Events	X	X	X	X	X	X	X	X	X	X	
Monitor for Serious Adverse Events	X	X	X	X	X	X	X	X	X	X	All SAEs must be collected from the date of subject's written consent until 42 days post discontinuation of dosing or completion of subject's participation in the study if the last scheduled visit occurs at a later time.
PK Assessments											
PK Sampling	X	X	X	X	X	X	X	X	X		See Table 5.5.3 for additional PK collection instructions.

Table 5.1-2: Short-Term Procedural Outline (IM128027)

Table 5.1-2: Short-Term Procedural Outline (IM128027)

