### 4.2 Secondary Efficacy Endpoint(s)

- Proportion of subjects who meet response criteria for the SLE Responder Index(4) [SRI(4)], SRI(5), SRI(6), and SRI(8) at Day 169
- Proportion of subjects who meet response criteria for the SLE Responder Index(4) [SRI(4)], SRI(5), SRI(6), and SRI(8) at Day 85
- Proportion of subjects with BICLA response at Day 85
- Change from baseline in CLASI score at Day 85 and Day 169

- Percentage of subjects with an improvement of at least 4 or an improvement of at least 50% from baseline in their CLASI score at Day 85 and Day 169
- Proportion of subjects with an improvement of at least 4 or an improvement of at least 20% from baseline in their CLASI score at Day 85 and Day 169
- Change from baseline in arthritis, as assessed by American College of Rheumatology (ACR) 28 joint counts of tender, swollen, and as well as active joints, i.e. those that are both tender and swollen at Day 85 and at Day 169
- The change from baseline in the following other indices SLE activity over time:
  - ◆ The overall BILAG-2004 score
  - ◆ The overall SLEDAI-2K score
  - ◆ The overall MDGA (Physician's Global Assessment of Disease Activity) score
- Change from baseline in SLICC/ACR Damage Index
- The cumulative corticosteroid and immunosuppressant use over time

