### **8.5 Day Ranges for Analysis of Time Points**

Subjects who do not always adhere strictly to the visit schedule timing in the protocol. Therefore the designation of visits during the Short-term period of the study will be based on the day of evaluation relative to the trial (day of first study medication = study Day 1) rather than the nominal visit recorded in the eCRF. Mutually exclusive relative day windows are defined below to provide derived visits that correspond to the post-baseline time points. If a visit falls outside of the pre-specified visit windows, then the data collected at that visit will not be assigned a derived visit but will remain in the derived data sets. Determination of baseline values is addressed in [Section 8.2](#).

If a subject has more than 1 visit where a measurement is recorded within a window, the measurement closest to the target day will be used. In case of 2 visits being equidistant from the target, the later measurement will be used in analyses. Exceptions to these rules apply to immunogenicity where the least favorable value (toward a positive response) in the window will be used.

For subjects who discontinue from study therapy prematurely, assessments performed after the last dose of the study drug will be included in the efficacy datasets provided that these assessments are made within 28 days of the last dose.

Designation of visits for efficacy assessments, immunogenicity samples and receptor occupancy samples during the Short-term period is tabulated below.

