**Table 8.5-1: Days Ranges for Assessments at Every Scheduled Visits During the Short-term Period**

Visit	Target Day	BILAG-2004, SLEDAI 2K, MDGA, PGA, ACR28, CLASI, SF-36, Coomb's test-direct	FACIT, C3, C4	SLICC	Anti-dsDNA	CRP, IgG, IgA, IgM	Immunogenicity (Anti-BMS-931699), Cytokines	ANA, Auto-antibodies
Baseline /Day 1	1		1	1	1	1	1	1
D15	15			8-21			8-21	
D29	29		15-43	22-43		15-43	22-57	15-43
D57	57		44-71	44-71		44-71		
D85	85		72-99	72-99		72-99	72-99	58-127
D113	113		100-127	100-127		100-127		72-99
D141	141		128-155	128-155		128-155		
D169	169		156-190*	156-190*	156-190*	156-190*	156-190*	156-190*

\* For subjects who enroll in long-term extension (LTE) period, the upper inclusive limit of this window is the start of LTE dose.

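### SAP 8.1.1 and 8.1.2: read literally, the 28-day limit for imputing a single missing component equals the visit spacing and leaves no room for the ±2-day visit window (minor)

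*SAP*

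**What the plan says.** SAP 8.1.1 (BICLA) and 8.1.2 (SRI(X)) use the same rule when exactly one component is missing at an efficacy visit for a reason other than premature discontinuation.

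- Before Day 169, the component is imputed from "the immediate previous efficacy visit and the immediate next efficacy visit within 28 days of the current visit date".
- At Day 169, it is imputed from "the previous 2 consecutive efficacy visits (within 56 days".
- If the component was met at both of those visits, it is imputed as met. "Otherwise, response status will be set to non-responder". A closing sentence in each section also sets any composite status that remains undetermined to non-response.

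On timing, Protocol 1.3.2 lists "The other indices of SLE activity measured at Days 29, 57, 85, 113, 141 and 169 including" the overall BILAG-2004, SLEDAI-2K and MDGA scores. Protocol Table 5.1-2 states that ± "2 days is allowed for all visits, including Day 1". SAP 8.5 assigns visits by actual study day: "Mutually exclusive relative day windows are defined below to provide derived visits that correspond to the post-baseline time points". These windows are in Table 8.5-1.

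SAP 4.2 lists "Proportion of subjects with BICLA response at Day 85" as a secondary endpoint, together with SRI(X) at Day 85.

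**The concern.** The limit equals the nominal spacing between efficacy visits, so it has no slack. Two visits that both keep to the protocol can be 29 to 32 days apart. The rule as worded then refuses the neighbour, and the missing component becomes a failure even if it was met on both sides. Response status would turn on one to four days of permitted scheduling, not on disease activity.

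The wording can also be programmed in two ways. The 28 days may qualify both neighbours or only the next visit, and the two versions classify some subjects differently.

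At stake are the Day 85 BICLA and SRI(X) rates and the same rates at other visits before Day 169. The primary endpoint is at stake only if the 56 days in the Day 169 rule is coded as a limit on actual dates.

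**Working it through.** The plan gives no figure for this rule. Its power statement (SAP 5) reproduces: 90.0% against at least 89%, and 75.0% against 74%. The calculation does not involve missing components, so it is not in question here.

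**Inputs from the documents.** Efficacy visits at Days 29, 57, 85, 113, 141 and 169; ±2 days at each; limits of 28 and 56 days; 70 subjects per arm.

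**1. Compliant gaps.** Nominal spacing is 57 − 29 = 85 − 57 = 113 − 85 = 141 − 113 = 169 − 141 = 28 days. The actual gap is 28 + (later offset − earlier offset), with offsets from −2 to +2. The range is 28 − 4 = 24 to 28 + 4 = 32 days. Gaps of 24 to 28 days pass the limit and gaps of 29 to 32 days fail it.

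**2. Day 169.** 169 − 113 = 56 days nominal, and 52 to 60 with the windows. If 56 days is a date limit, 57 to 60 fail. The Day 141 visit is always inside it.

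**3. The SAP's own visit windows.** For the BICLA component assessments, Table 8.5-1 accepts Days 44–71 as Day 57, 72–99 as Day 85 and 100–127 as Day 113. Adjacent derived visits can be 99 − 44 = 55 or 127 − 72 = 55 days apart. A visit can therefore be a valid derived neighbour and still be refused for imputation.

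**4. How often a compliant pattern is blocked at Day 85.** The documents give no distribution of visit dates. Assume independent offsets, a share p on target, and the remainder split equally over −2, −1, +1 and +2.

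- Limit on the next visit only: P(gap > 28) = (1 − P(equal offsets)) / 2. With p = 0.8 the other offsets have probability 0.05 each, P(equal) = 0.8² + 4 × 0.05² = 0.65, and the result is 0.175.
- Limit on both neighbours: let a, b and c be the Day 57, Day 85 and Day 113 offsets. Imputation is allowed when a ≥ b and c ≤ b. With p = 0.8 this is 0.8 × 0.9 × 0.9 + 2 × (0.05 × 0.95 × 0.10 + 0.05 × 1 × 0.05) = 0.6625, so 0.3375 is blocked.

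**5. Subjects affected per arm.** N = 70 × m × r × P(blocked), where m is the share with exactly one missing component and r the share who would otherwise respond. Neither is in the documents. The table uses m = 5% and r = 50%, and takes every such subject to have met the component at both neighbours.

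| Visits on target | Blocked, both bound | Of 70 | Blocked, next only | Of 70 |
|---|---|---|---|---|
| 100% | 0% | 0 | 0% | 0 |
| 90% | 18.4% | 0.32 | 9.4% | 0.16 |
| 80% | 33.8% | 0.59 | 17.5% | 0.31 |
| 20% (uniform) | 72% | 1.26 | 40% | 0.70 |

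With m = 1% and r = 25%, the 80% row with both bound gives 70 × 0.01 × 0.25 × 0.3375 = 0.06 subjects.

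**6. Day 169, only if 56 days is a date limit.** One gap matters (Day 113 to Day 169), so the next-only columns apply: 0.31 of 70 at 80% on target and 0.70 with uniform offsets.

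**7. Effect on a difference.** Borrowing the design rates of 50% and 25% for Day 85, a 25-point difference becomes 25 × (1 − 0.05 × 0.3375) = 24.6 points, or 25 × (1 − 0.05 × 0.72) = 24.1 with uniform offsets.

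**The case against.** The strongest reply is that the 28 days may only describe the nominal schedule, as the 56 days in the next bullet probably does. The SAP does not say outright what happens when a neighbour lies beyond the limit. Non-response follows from the otherwise-clause and from the closing fallback. This stands in part, and it is why the point is put as a literal reading. But the 28 days is tied to the date of the current visit, which is the language of a limit, and a programmer could reasonably code it so.

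A second reply is that a limit near four weeks suits the instruments. Protocol 5.4.2.1 has BILAG judge change over the preceding four weeks, and Protocol 5.4.1.1 names the 30-day SLEDAI-2K. The SAP does not give this reason, but some proximity limit is sensible. That is an argument for adjusting the limit, not for leaving it without slack.

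A third reply is that the consequence is negligible. This largely stands. The rule acts only with exactly one missing component, it is conservative, and SAP 7.5.2 plans no p-values for the Day 85 endpoints.

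A reader might also infer that the futility interim is distorted, because it uses Day 85 BICLA. The documents do not support resting the case there. The separate Interim Analysis SAP is not available and may set its own rule. Subjects who have only just reached Day 85 have no Day 113 visit, so imputation from two neighbours is closed to them whatever the limit.

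**Conclusion.** The point holds as a minor one. Read literally, SAP 8.1.1 and 8.1.2 reject neighbouring visits that comply with the protocol, and they do not say which neighbours the limit binds. Under the assumed inputs (5% with one missing component, 50% otherwise responders, 80% of visits on target, both neighbours bound), about 0.6 of 70 subjects per arm lose response status at Day 85. If all visits are on target, none do.

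These figures are illustrations, not bounds, because the documents give neither a missing-component rate nor a distribution of visit dates. The error runs towards non-response and the rule is the same in every arm, so any effect on a treatment difference is a slight shrinkage.

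A reader might infer that the primary analysis is compromised. The text does not show that. The 56 days names no reference date and probably just describes Days 113 and 141. Only if it is programmed as a limit on actual dates does a compliant gap of 57 to 60 days produce non-response at Day 169.

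**What to change.** Keep a proximity limit, but align it with the visit windows. In 8.1.1 and 8.1.2, state that:

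- before Day 169, both neighbours must be the adjacent scheduled efficacy visits, each within 32 days (28 + 2 + 2) of the current visit;
- at Day 169, the visits used are Day 113 and Day 141, both within 60 days (56 + 2 + 2);
- a neighbour outside the limit leads to non-response, if that is the intention.

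These limits admit every compliant pattern.

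The alternative is to define neighbours by derived visit under Table 8.5-1 and drop the day limits. That is simpler to program but gives up proximity. Adjacent derived visits from Day 57 to Day 113 can be up to 55 days apart. Day 113 and Day 169 can be up to 190 − 100 = 90 days apart in subjects who do not enter the extension. If this route is chosen, the SAP should acknowledge that response may then be imputed from more distant data.

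Either way the cost is a rewording of the imputation bullets in two SAP sections. It needs no new data and changes neither the endpoints nor the sample size.
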